#### 2.1.1.7 Visit Windows

Visit windows will be applied for all measurements except SANDE scores. Only one SANDE per day within a programmed window (5:00pm -11:59pm) can be entered into eDiary. If the subject does not complete the assessment within this window, the SANDE score will be missing for that day.

Table 2-1	Part 1: Allocation of assessments to analysis visit window
-----------	--

Scheduled main visit	Target study day	Analysis visit window in study	Visit Label
name		days	
Visit 1(D1)			
Visit 2(D14)			
Visit 3(D28)			
Visit 4(D42)			
Visit 5(D56)			

Table 2-2         Part 2: Allocation of assessments to analysis visit window			
Scheduled	Target study	Analysis visit	Visit Label
main visit	day	window in study	
name		days	
Visit 1(D-14)	-14	≤ -1	Screening
Visit 2(D1)	1	1	Baseline
Visit 3(D7)	7	2 – 11	Day 7
Visit 4(D14)	14	12 – 21	Day 14
Visit 5(D28)	28	22 - 35	Day 28
Visit 6(D42)	42	36 - 63	Day 42
Visit 7(D84)	84	≥ 63	Day 84

For both Part 1 and Part 2:

- If no measurement is available within a visit window, the assessment will be considered missing for the visit.
- If there is more than one measurement available within the same visit window, use the following rules:
  - 1. The record closest to the target day will be used.
  - 2. If there are multiple records with the same distance to the target day, the latest record will be used.
  - 3. If there are multiple records with the same distance on the same day, the average will be used.

Novartis	For business use only	Page 13
SAP		CECF843A2201

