Subjects will again be asked to sign the informed consent form in order to participate in Part 2 and will be re-screened to determine continued eligibility. If the subject meets all entry criteria, the subject may be randomized to receive either ECF843, at the concentration and posology selected from Part 1, or Vehicle at the same selected posology at a 3:1 ratio for 84 days of treatment. Enrollment for Part 2 of the study will be discussed between the Investigator and the Sponsor prior to initiating screening visits.

Screening: Subjects will be screened for eligibility at Part 2 Visit 1.

Run-in period: Screened subjects will enter a 14-day vehicle run-in period after screening.

**Randomization**: At Part 2 Visit 2 (baseline), subjects must screen for eligibility criteria at Visit 2 again. Only eligible subjects will be randomized into the study treatment. The randomization will be stratified by subjects with a documented diagnosis of Sjogren's syndrome (yes/no). Subjects will be equally randomized to study treatment.

**Treatment period**: The randomized subjects will begin 12 weeks study treatment after randomization. They will attend the following study visits after baseline for treatment: at Day 7, Day 14, Day 28, Day 42 and Day 84. Day 84 is the time point for primary analysis.

Part 2 is double-masked and exploratory. No interim analyses will be performed in Part 2.

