#### 2.1.1.6 Unscheduled visits

Unscheduled visit measurements will be included in the following:

- 1. derivations of measurements at scheduled visits per specified visit windowing rules below.
- 2. derivations of baseline/last on-treatment measurements.
- 3. derivations of the maximum/minimum on-treatment values and maximum/minimum changes from baseline values for safety analyses.
- 4. subject data listings where appropriate.

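### Part 2 visit windows put Day 63 in both the Day 42 and Day 84 visits, and the SAP does not say whether exams after the last dose count as Day 84

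*SAP*

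**What the plan says.** SAP 2.1.1.7 applies windows to everything except the daily symptom score: "Visit windows will be applied for all measurements except SANDE scores". The last three rows of Table 2-2 (Part 2) read:

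- "Visit 5(D28) 28 22 - 35 Day 28"
- "Visit 6(D42) 42 36 - 63 Day 42"
- "Visit 7(D84) 84 ≥ 63 Day 84"

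Selection among competing records is governed by a rule limited to one window: "If there is more than one measurement available within the same visit window, use the following rules". The first criterion is "The record closest to the target day will be used"; ties go to the latest record, and same-day ties are averaged.

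SAP 2.1.1.6 brings unscheduled exams into the "derivations of measurements at scheduled visits per specified visit windowing rules below". SAP 2.1.1.3 treats everything after the first randomised dose as post-baseline. SAP 2.1.1.5 defines a treatment end date for Part 2, but the visible text does not use it to limit any window. SAP 1.1.2 says of Part 2 that "Day 84 is the time point for primary analysis", and calls Part 2 exploratory.

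In the protocol, section 6.1 sets Part 2 masked treatment at 84 days. Section 8 asks for a full final-visit exam as soon as possible after early exit. Section 9.1.1 asks subjects who stop treatment to keep attending.

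**The concern.** Two windows that share a day leave the allocation of that day's exam undefined. A programmer must either pick a window without guidance or let one exam serve twice. In the second case a nine-week value appears in the summary of the twelve-week time point and also at Day 42.

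The open upper end raises a different question. The protocol (12.7) describes the Part 2 analysis as exploring efficacy and safety after 12 weeks of treatment. If an exam made some time after the last dose is the nearest one available, the table labels it Day 84. Whether that is intended is not stated. It should be settled before Part 2 results are seen, so that the choice cannot depend on them.

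**Working it through.** **Inputs.** Targets 7, 14, 28, 42, 84 and windows 2–11, 12–21, 22–35, 36–63, ≥63 (SAP Table 2-2). Treatment length 84 days (protocol 6.1). Post-treatment visits at Days 126, 154, 182 and 210 (protocol Table 8-2).

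**Step 1: rebuild the limits.** Upper limit = midpoint of adjacent targets, half-days rounded up. Next lower limit = that upper limit + 1.

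| Targets | Midpoint | Upper: computed / printed | Next lower: computed / printed |
|---|---|---|---|
| 7, 14 | (7+14)/2 = 10.5 | 11 / 11 | 12 / 12 |
| 14, 28 | (14+28)/2 = 21 | 21 / 21 | 22 / 22 |
| 28, 42 | (28+42)/2 = 35 | 35 / 35 | 36 / 36 |
| 42, 84 | (42+84)/2 = 63 | 63 / 63 | **64 / 63** |

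Seven of the eight limits are reproduced. Only the lower limit of Day 84 departs from the pattern.

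**Step 2: look for overlaps and gaps.** Counting windows for each study day from 2 to 219, Day 63 is the only day in two windows, and no day is in none.

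**Step 3: can distance decide?** |63 − 42| = 21 and |84 − 63| = 21. It cannot.

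**Step 4: apply the selection rules to example exam days.**

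| Exam days | As printed: Day 42 / Day 84 value from | With ≥64: Day 42 / Day 84 value from |
|---|---|---|
| 7, 14, 28, 63 | 63 / 63 | 63 / missing |
| 7, 14, 28, 42, 63 | 42 / 63 | 42 / missing |
| 7, 14, 28, 42, 63, 84 | 42 / 84 | 42 / 84 |
| 7, 14, 28, 42, 100 | 42 / 100 | 42 / 100 |
| 7, 14, 28, 42, 126 | 42 / 126 | 42 / 126 |
| 7, 14, 28, 42, 84, 126 | 42 / 84 | 42 / 84 |
| 7, 14, 28, 42, 63, 106 | 42 / 63 | 42 / 106 |

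The first row shows the double use. The rows with a Day 84 exam show that the closest-record rule protects anyone seen on target. The rows ending at Day 100, 126 and 106 show that the new lower limit does nothing about the open upper end. In the last row it even moves the Day 84 value from Day 63 to Day 106.

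**Step 5: how could double use arise?** In the visible rows of protocol Table 8-2, tear break-up time is marked at Visits 1, 2, 5 and 7, and visual acuity at Visits 2 and 7. Neither is marked at Visit 6 (Day 42). For these two measures a Day 63 early-exit exam would normally be the only record in both windows, even if Visit 6 was attended. For staining, which is scheduled at Visit 6, double use also needs Visit 6 to have been missed or to have fallen on Day 63 itself.

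**Step 6: where could post-treatment values come from?** The visible rows for Days 126 to 210 mark only concomitant medications and adverse events. The sources are therefore a late Visit 7, an unscheduled exam, an early-exit exam on Day 63 or later, or attendance after stopping treatment.

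**The case against.** The strongest reply is that little can go wrong in practice. Day 63 is not a scheduled day, and protocol section 8 tells sites to steer later visits back to their original dates. No tear break-up or visual acuity result is planned for Day 42, so there is no planned result to duplicate. This limits how often the overlap matters. It does not resolve the overlap, and an unplanned Day 42 entry for those two measures could still be produced.

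On the open upper end, the reply has more force. A late Visit 7 need not be off treatment, because section 8 asks sites to resupply subjects who cannot keep the schedule. An open last window keeps such data. SAP 2.13 uses observed data with no visible on-treatment restriction, so including post-treatment values may be deliberate. All of that stands; what remains is that the SAP does not say so.

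A reader might infer three stronger points that the documents do not support:

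- That the follow-up visits to Day 210 routinely feed the Day 84 window. The visible schedule has no windowed eye exams there, although some rows may be redacted.
- That an upper limit would keep off-treatment values out. A window of 64–105 would still admit exams on Days 85–105 after the last dose. It would also admit a subject who stopped on Day 50 and attended on Day 84.
- That Day 11 is misallocated because it is 4 days from Day 7 and 3 from Day 14. The midpoint is 10.5, and the 11/12 split has neither overlap nor gap. Moving it would be a preference.

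**Conclusion.** The Day 63 overlap is a definite, isolated slip in a stated rule. The missing statement on post-treatment exams is a genuine gap in the visible text, though not evidence of a wrong choice.

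Both are small. Double use needs an exam on exactly Day 63 with no closer record in either window. Mislabelling a post-treatment exam needs the absence of any exam nearer Day 84. The documents give no rate for either, so no count can be estimated; the ceiling is the 160 subjects planned for Part 2, and the realistic number is a few. The word primary in the SAP's description of Day 84 might suggest that a confirmatory result is at risk. It is not: the primary and secondary objectives listed all belong to Part 1, Part 2 is exploratory, and the symptom score is exempt from windowing.

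This rests on the public text. The Part 1 limits in Table 2-1 are blank there and were not judged.

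**What to change.** 1. In SAP Table 2-2, change the Day 84 lower limit from ≥63 to ≥64. Each study day from Day 2 on then falls in exactly one window. This is a one-character edit plus the matching program line. The cost is that a subject whose last exam is on Day 63 has no Day 84 value. Early values are not otherwise removed: a Day 64 exam, 84 − 64 = 20 days early, still counts as Day 84.
2. Add a sentence to SAP 2.1.1.7 saying whether exams after the Part 2 treatment end date (SAP 2.1.1.5) count towards Day 84. Either answer is workable. Excluding them costs some observed data; including them should be reflected in how the Day 84 result is described.
3. Optionally, cap the window, for example at Day 105, since (84 + 126)/2 = 105. This follows the table's midpoint pattern but is a choice: it discards some late data and does not replace item 2.

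Leave the Day 7 and Day 14 windows as they are. Make the changes before Part 2 is unmasked.

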#### 2.1.1.8 Change from baseline for continuous parameters

Change from baseline will only be summarized for subjects with both baseline and postbaseline values and will be calculated as:

change from baseline = post-baseline value – baseline value

For summary statistics the raw values (and not imputed values) will be used.

#### 2.1.1.9 Study eye

Study eye is defined as the eye with the highest composite corneal staining score at baseline. If both eyes have equal composite corneal staining scores, then the right eye will be selected as the study eye. The other eye will be fellow eye. All the efficacy endpoints will be based on the study eye if laterality applies. The safety analysis will be presented for both eyes.

#### 2.2 Analysis sets

#### Part 1

- The All Enrolled Set 1 (ENS1) includes all subjects who signed informed consent for Part 1. This analysis set will be used to summarize patient disposition.
- The Full Analysis Set 1 (FAS1) comprises all subjects

According to the intent to treat principle, subjects will be analyzed according to the treatment and strata they have been assigned to during the randomization procedure.

FAS1 will be used for all efficacy analyses, unless otherwise stated.

• The Safety Set 1(SAF1) includes **according** who received at least one dose of study treatment. Subjects will be analyzed according to the study treatment received, where treatment received is defined as the actual randomized treatment if the subject took at least one dose of that treatment or the first treatment received if the randomized treatment was never received.

# 

#### Part 2

- The All Enrolled Set 2 (ENS2) includes all subjects who signed informed consent for Part 2. This analysis set will be used to summarize patient disposition.
- The Full Analysis Set 2 (FAS2) comprises all subjects to whom study treatment has been assigned by re-randomization in Part 2. According to the intent to treat principle, subjects will be analyzed according to the treatment and strata they have been assigned to during the randomization procedure.
- The Safety Set 2 (SAF2) includes all subjects who received at least one dose of study treatment in Part 2. Subjects will be analyzed according to the study treatment received,

where treatment received is defined as the re-randomized treatment if the subject took at least one dose of that treatment or the first treatment received if the re-randomized treatment was never received.

Rules of exclusion criteria of analysis sets with protocol deviations and subject classification are specified in Appendix 5.3. Rule of exclusion of subjects for analysis are specified in Appendix 5.4.

#### 2.2.1 Subgroup of interest

The subgroups of interest are specified below:

- Baseline age group: < 65 years, and >=65 years
- Sex: male, female
- Documented diagnosis of Sjogren's syndrome: yes, no
- Race: asian, non-asian

# 2.3 Subject disposition, demographics and other baseline characteristics

Subject characteristics and study conduct summaries include tables and listings such as subject disposition table, demographics and baseline characteristics tables, summary of screen failures by reason and listing of subjects excluded from analysis sets.

# 2.3.1 Subject disposition

Subject disposition table will be reported for ENS1 and ENS2.

In addition, the number and percentage of subjects who completed the study, discontinued from the randomized treatment/study by the reason of discontinuation, will be summarized by treatment and total. Percentages will be based on the number of subjects in FAS1 and FAS2.

Subjects who prematurely discontinue the randomized study treatment (treatment period) will be listed along with the reason for discontinuation.

In addition, protocol deviations (PDs) will be summarized through presenting the number and percentage of subjects with each deviation for FAS1 and FAS2.

#### 2.3.2 Demographics and baseline characteristics

Demographic table will include age, sex, race, ethnicity, ancestry, eye color, Sjögren's Syndrome status.

Baseline characteristics table will include:

• SANDE score

- conjunctival lissamine staining score
- corneal fluorescein staining score
- intraocular pressure (IOP)
- tear break-up time (TBUT) average score
- schirmer score
- conjunctival redness

Demographic and baseline characteristics will be summarized for FAS1 and FAS2 populations by treatment group for study eye.

Categorical data will be presented as frequencies and percentages. For continuous data, mean, standard deviation, median, 25th and 75th percentiles, minimum, and maximum will be presented.

Relevant medical histories and current medical conditions at baseline will be summarized by system organ class, preferred term and treatment group separately for ocular and non-ocular histories/conditions.

# 2.4 Treatments (study treatment, rescue medication, concomitant therapies, compliance)

The SAF 1 and SAF 2 will be used for the analyses below. Categorical data will be summarized as frequencies and percentages. For continuous data, mean, standard deviation, median, minimum, and maximum will be presented.

#### 2.4.1 Study treatment / compliance

The duration of exposure in days to randomized study treatment will be summarized by means of descriptive statistics by treatment group. The duration of exposure is defined as: date of the last administration of randomized study treatment (end of treatment date) – date of first administration of randomized study treatment +1 (Section 2.1.1.1).

Compliance will be presented by summarizing the total number of days with missing dose or dose interrupted within the randomized treatment period by treatment group. Reason of premature discontinuation from the randomized study treatment will also be summarized.

#### 2.4.2 **Prior**, concomitant and post therapies

Prior medications are defined as drugs taken and stopped prior to the first administration of randomized study treatment (Section 2.1.1.2). Any medication given at least once between the day of the first administration of the study treatment and the EORT Visit will be a concomitant medication, including those that were started pre-baseline visit and continued into the treatment period. Post therapies are defined as drugs taken after EORT Visit, including those taken prior to EORT Visit and continued until the end of study. Prior, concomitant medication and post therapies will be identified based on recorded or imputed start and end dates of taking the medication.

Prior, concomitant medication or post therapies will be summarized by treatment group (separately for ocular and non-ocular medications/therapies), presented in alphabetical order by ATC classification codes and preferred term. The tables will be presented with overall number and percentage of subjects receiving at least one drug of a particular ATC code and at least one drug in a particular preferred term. Medications will be coded according to the WHO Drug Reference List dictionary.

In addition, all information will be listed including the reported name, laterality, and treatment start/end date, etc.

# 2.4.2.1 Rescue medication

The number and percentage of subjects who received artificial tears/gels/lubricants for occasional rescue use during treatment period will also be summarized by treatment group.

#### 2.4.2.2 Prohibited medication

Moreover, concomitant medications that are prohibited as per protocol (Table 2-3) during the conduct of the study will be summarized specifically. The number and percentage of subjects who used prohibited medications during treatment period will be summarized by treatment group.

Medication	Prohibition period	Action taken
Ocular, nasal, inhaled, or systemic corticosteroids	During the study	Do not discontinue study treatment but document use of the product in the eCRF
Any topical ocular medications (prescription or over-the- counter; excluding IOP- lowering medication)	During the study	Do not discontinue study treatment but document use of the product in the eCRF If the addition of a medication is needed for treatment of an adverse event, the decision to discontinue study treatment will be made by the Investigator and Sponsor based on the relevance and duration of the prohibited treatment
Intravitreal injections of any kind	During the course of the study	Do not discontinue study treatment, but document use of the product in the eCRF If the addition of a medication is needed for treatment of an adverse event, the decision to discontinue study treatment will be made by the Investigator and Sponsor based on the relevance and duration of the prohibited treatment

Table 2-3Prohibited medication

Medication	Prohibition period	Action taken
Medical device treatments such as those used to treat Meibomian gland dysfunction (e.g., LipiFlow, pulse light therapy, etc.)	During the study	Discontinue study treatment
Punctal plugs or punctal cauterization	Placement of new occlusion during the course of the study	Discontinue study treatment

# 2.5 Analysis of the primary objective

The primary aim of the study is to demonstrate improvement in moderate to severe DED with ECF843. This will be evaluated by measuring signs and symptoms as primary estimands.

The symptoms measure of SANDE questionnaire is completed through an electronic diary every evening before bedtime during the study. The signs measure of corneal fluorescein staining will be conducted by the Investigator during site visits based on the Corneal Fluorescein Modified NEI Scale.

For the purpose of the statistical analyses presented in this document, the following terminology is used:

• Jump to Reference (J2R) – the multiple imputation model will be build based on the available vehicle data (including partial information from patients that discontinued prematurely). The imputation model will include important background characteristics and observed data.

• Missing at Random (MAR) – the multiple imputation model will be build based on similar patients (i.e. with the same covariates and observed measurement history) in the same treatment arm.

• Retrieved drop-out (RDO) patients - Patients who discontinue study treatment and decide to remain in the study by following an abbreviated schedule of assessments.

• Intercurrent events (IE) - Events that occur after treatment initiation and either preclude observation of the variable or affect its interpretation (e.g., rescue medications, discontinuation of treatment, switching treatment, terminal events such as death, etc.)

#### 2.5.1 Primary endpoints

The primary clinical question of interest is: What is the effect of ECF843 versus its corresponding vehicle on change from baseline in signs and symptoms after treatment in subjects with moderate to severe DED, had they not taken occasional rescue use of artificial tears/gels/lubricants, prohibited medications and behaved like other subject who did not take them, had they not dicontinued treatment and behaved like other subjects who did not discontinue treatment?

The justification for the primary estimands is that they will capture the effect of the study drug when administered without confounding effects from prohibited medications, occasional

rescue use of artificial tears/gels/lubricants, and adjusting for unfavorable outcome treatment discontinuation

The analysis of the primary estimands will be based on FAS 1.

The primary estimand is defined as follows for signs and symptoms:

- The target **population** is subjects with moderate to severe DED who meet the inclusion and exclusion criteria
- The primary **endpoints** are the change from baseline in SANDE score and change from baseline in composite corneal fluorescein staining score
- The **treatment of interest** is ECF843 versus vehicle had they not needed occasional rescue use of artificial tears/gels/lubricants, prohibited medications and behaved like other subjects who did not take them, and had they not dicontinued treatment and behaved like other subjects who did not discontinue treatment.

Table 2-4	The handling of intercurrent events strategy for primary estimands
-----------	--

Intercurrent Events	Strategy
Artificial tears/gels/lubricants for occasional rescue use	
 
The data on the days will be excluded and treated as missing.
 

	
 
Missing data will be under MAR assumption in MMRM
 

 
Prohibited medications that could confound the primary endpoint (See Table 2-3)
 
Ocular, nasal, inhaled, or systemic corticosteroids
 
	
 
The data on the day(s) + 3 days following the last day of these prohibited medications will be excluded and treated as missing.
 

Intravitreal injections of any kind	
 
Missing data will be under MAR assumption in MMRM
 

 
Any topical ocular medications (prescription or over the counter; excluding IOP-lowering medication)
 
	
 
The data on the days of prohibited medications will be excluded and treated as missing.
 


 
Medical device treatments such as those used to treat Meibomian gland dysfunction (eg, LipiFlow, pulse light therapy, etc)
 
	
 
Missing data will be under MAR assumption in MMRM
 

Punctal plugs or punctal cauterization	
Discontinuation of study treatment	
 
The data after study treatment discontinuation will be treated as missing.
 

	
 
Missing data after study treatment discontinuation will be based on the MAR assumption in MMRM
 

- The **summary measure** is the treatment difference of the variable means between ECF843 and vehicle within each dose regimen (BID or TID) respectively.
  - ECF843 0.45mg/ml, TID vs ECF843 vehicle, TID
  - ECF843 0.15mg/ml, TID vs ECF843 vehicle, TID

Novartis	For business use only	Page 19
SAP		CECF843A2201

• ECF843 0.15mg/ml, BID vs ECF843 vehicle, BID

